4.2.2 Secondary Outcome Measures

Secondary outcomes include:

- Code status preferences (Aim 1)
- Use of palliative care consult/services (Aim 1)
- Hospice use (Aim 1)
- Health Care Proxy (Aim 1)

Secondary outcomes related to Aim 2a (patients 18+ years admitted to one of the study inpatient units with ADRD/delirium) include:

- Documentation of ACP Preferences in Electronic Health Record

Secondary outcomes related to Aim 2b (caregivers of patients with ADRD/Delirium) include:

- ACP knowledge (Aim 2)
- Confidence in future care (Aim 2)
- Communication satisfaction (Aim 2)
- Decisional satisfaction (Aim 2)
- Decisional conflict (Aim 2)

5 Study Design

This is pragmatic SW-CRT of a PCE-led, video-assisted COVID-19 ACP intervention in inpatient-based units (3 medical-surgical wards, Medical ICU, Cardiac ICU, Neurology ICU, step-down unit) at two hospitals: BMC and North Shore University Hospital (Northwell Health). All inpatients ≥ 65 and all patients with ADRD/Delirium ≥ 18 who are hospitalized on a unit during the intervention phase will receive the intervention.

This 2-year study (2 month data collection and tool preparation, staff training and site standardization (we are already embedded in both health systems doing similar work; thus this

short timeframe is feasible); 16 months rolling recruitment and surveying; 2 months data cleaning and analysis, and 4 months manuscript preparation and dissemination of findings) will roll out the intervention to 14 randomized inpatient units at 2 sites. Every two months, an additional inpatient unit will be added to our intervention at each hospital, i.e., there will be seven waves or "steps"; for a total of 7 units at each hospital.

Consistent with a SW-CRT with two hospital units per step (cluster), prior to the collection of any data in the pre-intervention period, we will generate a set of uniform random numbers for each of the seven clusters to be assigned to a starting period for the study intervention. There will be eight study periods in total with a usual care period at the start of the study for all clusters. The first randomized intervention period will then begin in period two.

Cluster	Baseline	14 Months of Clustered Intervention Expansion							
	M0	M2	M4	M6	M8	M10	M12	M14	
1									
2									
3									
4									
5									
6									
7									

The data needed to assess the outcomes for all patients will be derived from each hospital's EHR (Aim 1).

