For Aim 2b, 600 caregivers of patients with ADRD/Delirium (300 control phase; 300 intervention phase) will be surveyed by telephone during (or within one week of) the index hospitalization to assess caregiver-centered outcomes.

Each day PCEs, who will be nurses or social workers on the palliative care team, will approach patients who are currently hospitalized under Aim 1 or Aim 2a. The PCE will then proactively use the goals-of-care video decision aid (or any of the additional videos regarding CPR, hospice, dementia, etc., as relevant and in the appropriate language) to provide educational support and assist in delivering primary palliative care services relating to goals-of-care conversations and ACP documentation. The videos range from 4-6 minutes in length and the PCE will watch the videos together with the patient and caregiver on an iPad (or remotely via telehealth with the caregiver).(130)

The PCE will arrange all video showings to include patient and caregiver (when possible and acceptable to the patient); when patients are unable to view a video (e.g., loss of capacity, delirium), the caregiver will view the video. The videos do not replace clinician counseling; indeed, they are designed to allow the PCE to confirm comprehension and to stimulate

conversation with a shared vocabulary. The PCE will then communicate the patient's or caregiver's wishes to the treating primary medical team to coordinate care.

In cases when the PCE deems that engagement with the full palliative care team is warranted, they will approach the treating primary medical team to place the consult. If/when the PCE exhausts the automated list for patients, they will coordinate with the palliative care consult team to select patients from the list of requested consultations. The PCE role will be fully integrated into existing hospital practices at our sites consistent with the pragmatic nature of this study design.

For Aim 1, the study population will consist of patients 65 years or older who are admitted to one of the study inpatient units in the hospital. For Aim 2a, the study population will consist of any patient ≥ 18 years admitted to one of the study inpatient units in the hospital with a diagnosis of ADRD/Delirium. For Aim 2b, the study population will consist of adult (≥ 18) caregivers of patients identified in Aim 2a. These caregivers will be recruited to complete a phone survey for our secondary caregiver outcomes

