7.1 Subject Inclusion Criteria

Over the two years of the trial, we will examine data on approximately 15,000 patients ≥ 65 admitted to these 23* units for our primary and secondary outcomes (Aim 1). Given the pragmatic nature of this trial, our inclusion criteria are quite broad and consistent with the goal of pragmatic trials.

We will also survey caregivers of 600 patients with ADRD/Delirium to conduct a telephone administered survey for caregiver-centered outcomes (knowledge, confidence, communication satisfaction, decisional satisfaction, and decisional conflict) during the index hospitalization. Caregivers may or may not be designated as ADRD/Delirium legal surrogate decision maker for the patient (i.e., most patients with ADRD/Delirium do not have a legally designated representative.) Any adult identified in the EHR as the contact family member or friend will be eligible to partake in the caregiver survey. Half of surveys will be conducted during the control period; half during the intervention period. Caregivers will be either English- or Spanish-speaking adults, which are the languages in which our surveys are validated. For patients in the control group, surveys will be completed during the hospital stay or within 1 week of discharge. For patients in the intervention group, the survey will be completed AFTER the PCE intervention, and up to 1 week after discharge.

*14 units (7 per hospital) will be included in the stepped wedge trial, an additional 9 units (3 at BMC and 6 at NorthShore) will be used to recruit additional control participants only. These additional units were added due to low recruitment at the start of the study and the decreasing number of control units as the stepped wedge design progresses. The target enrollment of 600 caregivers is still accurate.

Adding delirium to the list of eligible diagnoses will also increase the potential number of eligible subjects. The surveys are applicable to the caregiver of any patient who is not capable of making their own health decisions; this includes patients who are experiencing any sort of memory or cognitive decline.

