7.2 Subject Exclusion Criteria

For Aim 1, there are no exclusion criteria.

For Aim 2a, there are no exclusion criteria.

For Aim 2b, not speaking English or Spanish, which are the languages in which our surveys are validated.

- We will not be including individuals who are not yet adults (infants, children, teenagers)
-
- We will not be including prisoners

8 Study Intervention

A palliative care trained provider (a nurse or social worker on the palliative care team) will serve as the PCE. Using the ACP videos on a tablet via a Video App, the PCE will provide educational support and assist in delivering primary palliative care services relating to in-the-moment goals-of-care conversations and ACP documentation for patients that are hospitalized. PCEs will be members of the Palliative Care team, coordinate daily activities with the team, and report to the head of the Palliative Care service. PCEs will serve in a triage function to manage cases that can be handled with educational support for goals-of-care conversations and ACP documentation or to stimulate full palliative care consultation. PCEs will directly coordinate communication of the patient's preferences with the treating primary medical team. A key aspect of this trial design is the fully integrated role into existing hospital practices of the PCE position.

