Aim 2b: Study staff will contact identified adult caregivers by phone to describe the survey activity

Recruitment

For Aim 1, all patients over the age of 65 will be included in the trial. For those patients admitted to wards/units in the intervention phase, the PCE will proceed with primary palliative care and view the ACP videos with the patients and family. For patients over the age of 65 admitted to wards/units that are in the control phase, usual care will proceed without the use of the PCE.

For Aim 2a, we will identify 600 inpatients to the study units with ADRD/Delirium who are 18+ years old.

For Aim 2b, 300 caregivers of the patients identified in Aim 2a will be surveyed during the control phase, and 300 caregivers will be surveyed during the intervention phase. For the group of caregivers (N=600) being surveyed for caregiver-centered outcomes, individual verbal informed consent will be obtained. The RA will survey caregivers using a validated survey tool. For patients with ADRD/Delirium and their caregivers that are admitted to a ward/unit that has been randomized to the intervention, the PCE will proceed with the video intervention.

Recruitment efforts for the caregiver survey (Aim 2) will be limited to English- and Spanish-speaking caregivers who are able to independently consent to participate in a research study. Research staff will work with the care team on the inpatient units where identified patients are currently hospitalized. The health care team will locate (either in person or by phone) designated caregivers for identified patients and invite them to participate. A member of the care

team will approach the caregiver and ask if they would be interested in getting a phone call from the research team to get more information about the study. If the caregiver says yes, the RA will call them, read the recruitment script (attached), and, if the subject is willing, review the consent form and complete the survey. If the designated caregiver cannot be located to invite to participate, an invitation letter with opt-out postcard will be mailed to them.

Informed Consent

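### Section 7.1 places intervention-phase caregiver surveys after the PCE visit but does not say whether caregivers of patients the PCE never reaches are surveyed

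*Combined protocol and SAP*

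**What the plan says.** Section 7.1 gives a separate timing rule for each phase. For control: "For patients in the control group, surveys will be completed during the hospital stay or within 1 week of discharge". For intervention: "For patients in the intervention group, the survey will be completed AFTER the PCE intervention, and up to 1 week after discharge". Only the second depends on a care event.

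Eligibility does not mention that event. Section 7.1 says "Any adult identified in the EHR as the contact family member or friend will be eligible to partake in the caregiver survey", and the Aim 2b exclusion in Section 7.2 is "For Aim 2b, not speaking English or Spanish, which are the languages in which our surveys are validated". Prisoners and people who are not yet adults are also excluded.

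The intention is that everyone is reached. Section 5 says that eligible patients "hospitalized on a unit during the intervention phase will receive the intervention", and Section 9 (Recruitment) says that for patients with ADRD/delirium and their caregivers "admitted to a ward/unit that has been randomized to the intervention, the PCE will proceed with the video intervention". Section 5 also says what the PCE does if and when the automated patient list runs out, so finishing the list is not taken for granted. No reach rate is given.

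The survey window is worded in more than one way. One paragraph of Section 5 says caregivers "will be surveyed by telephone during (or within one week of) the index hospitalization to assess caregiver-centered outcomes". A later paragraph of Section 5 confines the survey to the index hospitalization. Section 7.1 first names the index hospitalization and then allows the extra week.

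Section 12.3 commits to intent-to-treat for the comparative analyses. It assigns patients who move units to intervention by time spent on an intervention unit (at least eight daytime weekday hours after being identified as eligible), not by PCE contact.

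**The concern.** When a patient leaves hospital without a PCE visit, the research assistant needs to know whether to call the caregiver. Read literally, the Section 7.1 timing rule says no, because there is no visit for the survey to follow. The eligibility text and the general window in Section 5 say yes. Two sites recruiting separately could settle this differently.

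If the literal reading is followed, being surveyed in the intervention phase requires something that happens after allocation, and nothing comparable is required in the control phase. The intervention sample would then hold only caregivers of reached patients, while the control sample would hold caregivers of patients who would and would not have been reached. Patients who are missed may well differ from those who are seen, for example in length of stay or in who is at the bedside, and so may their caregivers. Aim 2b would no longer compare caregivers by assigned phase. Adjustment and multiple imputation under Section 12.3 work on people in the dataset; they do not recover caregivers who were never approached.

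**Working it through.** **1. Does any section settle the case of an unreached patient?**

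| Text | What it settles | Covers caregivers of unreached patients? |
|---|---|---|
| 7.1 timing rule, intervention | Order: visit, then survey | No; read literally it leaves them out |
| 7.1 eligibility, 7.2 exclusions | Who may be surveyed | They are eligible; no timing is given |
| 5, window during or within a week of the stay | When surveys take place | Permits them, but does not address 7.1 |
| 12.3, unit-time rule | Group of patients who move units | Group only, not whether to survey |
| 12.3, intent-to-treat | How collected data are compared | Not whom to survey |
| 12.3, withdrawal from the intervention only | Continued data collection | No; it concerns participants already in the sample |

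The gap is real. Under the unit-time rule, a patient can be classed as intervention without having been seen.

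**2. How many caregivers could be omitted?**

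Inputs: 300 intervention-phase surveys (Section 9: "300 caregivers will be surveyed during the intervention phase"). Reach r and equal response among caregivers of reached and unreached patients are assumptions.

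If 300 surveys are completed among caregivers of reached patients, the corresponding pool is 300/r, and the number omitted is 300/r − 300 = 300(1 − r)/r.

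- r = 1.0 (the stated intention): 0
- r = 0.9: 300 × 0.1/0.9 = 33
- r = 0.8: 300 × 0.2/0.8 = 75

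None would be omitted from control by this rule.

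**3. What would the bias be?**

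With no intervention effect, and an SD gap g between caregivers of reached and unreached patients, surveying only the former shifts the intervention mean by (1 − r) × g. The documents give neither r nor g, nor the sign of g. As an illustration only, g = 0.3 gives 0.03 SD at r = 0.9 and 0.06 SD at r = 0.8; g = 0.5 gives 0.05 and 0.10 SD. These are not estimates.

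**4. What does surveying everyone cost in power?**

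The plan's own figure first. Section 12.2 states 90% power for an effect size of 0.53 with about 600 caregivers and a design effect of 2.03. Effective n per group = 300/2.03 = 147.8; SE = √(2/147.8) = 0.1163; detectable effect = (1.960 + 1.282) × 0.1163 = 0.377 SD. So 0.53 does not reproduce from these inputs. That is a separate matter, and the next step does not depend on it.

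For any effect with 90% power at full reach, effect/SE = 1.960 + 1.282 = 3.242. If caregivers of unreached patients gain nothing and the SE is unchanged, power = Φ(3.242r − 1.960):

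- r = 1.0: Φ(1.282) = 0.90
- r = 0.9: Φ(0.958) = 0.83
- r = 0.8: Φ(0.634) = 0.74

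**The case against.** The strongest reply is that the sentence in Section 7.1 is a sequencing rule. An outcome meant to reflect the intervention has to be measured after it, and neither the eligibility text nor the exclusions require PCE contact. Delivery is meant to be universal, group membership is by phase, and Section 12.3 keeps collecting data from participants who withdraw from the intervention. Harm therefore needs both incomplete reach and a literal application of the sentence. All of this stands, and it limits the point to a gap that needs closing.

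A reader might infer more than the documents support:

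- That the plan excludes caregivers of unreached patients. It does not say so; it is silent.
- That Section 7.1 contradicts the 300 + 300 targets or the one-week window in Section 5. It does not. The targets can be met by surveying someone else, and a survey after the visit and within a week of discharge satisfies both sections.
- That the loss would be invisible, or that contact and survey dates are not recorded. Neither is established. The Aim 2 counts listed in Section 12.3 have no line for unreached cases, but the same section commits to CONSORT reporting, and the chart review instrument attached to the protocol is not in the text available for review.
- That later survey timing in the intervention phase is itself an error. It is largely inherent in surveying after an intervention, and the change proposed here does not remove it.

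What the reply does not supply is an instruction for the unreached case. Intent-to-treat governs data already collected, and the withdrawal rule concerns people already in the sample.

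**Conclusion.** The point holds as a conditional gap in the Aim 2b procedures. If some patients are not reached and Section 7.1 is followed as written, caregivers are selected on a post-allocation event in one phase only. That is out of line with the intent-to-treat principle and with the unit-time assignment rule, and no later analysis step repairs it. If every patient is reached, or staff read the sentence as order only, there is no selection.

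No bias size or direction is claimed. The counts of about 33 and 75 omitted caregivers rest on 300 completed intervention surveys, equal response and an assumed reach of 90% or 80%. Aim 2b is secondary and the EHR-based primary outcome is unaffected. The change should be made because it is cheap and because the loss cannot be undone once the survey window has passed. Confidence is medium, since the documents give no reach rate.

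**What to change.** In Section 7.1:

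- State that Aim 2b eligibility and group depend on unit phase, not on receipt of the PCE intervention.
- Keep the after-PCE order where a visit occurs. Where none has occurred, survey the caregiver before the existing window closes 1 week after discharge.
- Give one survey window and reconcile the wording in Sections 5 and 7.1 with it.

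In Section 12.3, analyse all surveyed caregivers by assigned phase and report the contacted-only comparison as supportive. Record PCE contact (yes/no and date) and survey date if the forms do not already hold them.

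The cost is a clarifying amendment and at most a few data fields. The chart review in Section 9 already covers the patient of every surveyed caregiver and could hold the contact field where the PCE has documented in the EHR. Using the PCE tracking documents instead needs the IRB amendment that Section 8 foresees. If reach is incomplete, the effect by assigned phase is diluted, with the loss of power shown above. Surveys for caregivers of unreached patients will tend to fall late in the window, so survey timing should be reported by phase.

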7.2 Subject Exclusion Criteria

For Aim 1, there are no exclusion criteria.

For Aim 2a, there are no exclusion criteria.

For Aim 2b, not speaking English or Spanish, which are the languages in which our surveys are validated.

- We will not be including individuals who are not yet adults (infants, children, teenagers)
-
- We will not be including prisoners

8 Study Intervention

A palliative care trained provider (a nurse or social worker on the palliative care team) will serve as the PCE. Using the ACP videos on a tablet via a Video App, the PCE will provide educational support and assist in delivering primary palliative care services relating to in-the-moment goals-of-care conversations and ACP documentation for patients that are hospitalized. PCEs will be members of the Palliative Care team, coordinate daily activities with the team, and report to the head of the Palliative Care service. PCEs will serve in a triage function to manage cases that can be handled with educational support for goals-of-care conversations and ACP documentation or to stimulate full palliative care consultation. PCEs will directly coordinate communication of the patient's preferences with the treating primary medical team. A key aspect of this trial design is the fully integrated role into existing hospital practices of the PCE position.

PCEs will receive Vital Talk intensive communication skills training via a highly structured series of Zoom conferences. The PCEs will also be trained on use of the ACP certified videos using the ACP App. Training will instruct clinicians on how to: 1. Introduce the videos to patients and caregivers; 2. Use the videos as adjuncts to ACP counseling by clinicians; 3. Select the appropriate video(s) from the entire suite according to patients' needs; and, 4. Prescribe videos for patients and caregivers using the electronic platform. The suite of ACP videos is designed to address common ACP decisions confronting patients at risk or with COVID-19 and their caregivers. The videos also cover all of the decision points surrounding ADRD/Delirium (e.g., feeding tubes, resuscitation, etc.). The videos are intended to be an adjunct to clinician counseling, not to replace it. Suggested videos for clinicians to use with patients will include goals-of-care videos, general ACP videos, intervention-specific videos such as ventilatory support or CPR, and hospice videos. PCEs will also have an array of videos to support caregivers, including videos regarding compassionate extubation if this is relevant.

The PCE will encourage the patient to make their wishes known to their family or other caregiver (and will offer to facilitate a call/video-call) and the attending, and that with the patient's

permission, will relay their wishes to the treating team in addition to completing ACP documentation in the EHR. As an integrated part of existing hospital practice, PCE will communicate with the primary treating team and the palliative care team. When there are palliative care needs beyond ACP (e.g., symptom control) or if the PCE determines that the support of the full palliative care team is warranted, the PCE will recommend to the treating team to place the consult request. The PCE will not be collecting any data for research purposes only. For QI purposes, the Palliative care consult team will keep tracking documents of the PCE activities (number of patients seen per day, amount of time spent with each patient, etc). This is needed for supervisory purposes. These may be reviewed retrospectively by the research team and compared to research data. In this case, an amendment will be submitted to the IRB to cover these activities.

9 Study Procedures

Eligibility

Aim 1 and Aim 2a: Each day, PCEs will review a list of inpatients who are ≥ 65 or have a diagnosis of ADRD/Delirium

Aim 2b: Study staff will contact identified adult caregivers by phone to describe the survey activity

Recruitment

For Aim 1, all patients over the age of 65 will be included in the trial. For those patients admitted to wards/units in the intervention phase, the PCE will proceed with primary palliative care and view the ACP videos with the patients and family. For patients over the age of 65 admitted to wards/units that are in the control phase, usual care will proceed without the use of the PCE.

For Aim 2a, we will identify 600 inpatients to the study units with ADRD/Delirium who are 18+ years old.

For Aim 2b, 300 caregivers of the patients identified in Aim 2a will be surveyed during the control phase, and 300 caregivers will be surveyed during the intervention phase. For the group of caregivers (N=600) being surveyed for caregiver-centered outcomes, individual verbal informed consent will be obtained. The RA will survey caregivers using a validated survey tool. For patients with ADRD/Delirium and their caregivers that are admitted to a ward/unit that has been randomized to the intervention, the PCE will proceed with the video intervention.

Recruitment efforts for the caregiver survey (Aim 2) will be limited to English- and Spanish-speaking caregivers who are able to independently consent to participate in a research study. Research staff will work with the care team on the inpatient units where identified patients are currently hospitalized. The health care team will locate (either in person or by phone) designated caregivers for identified patients and invite them to participate. A member of the care

team will approach the caregiver and ask if they would be interested in getting a phone call from the research team to get more information about the study. If the caregiver says yes, the RA will call them, read the recruitment script (attached), and, if the subject is willing, review the consent form and complete the survey. If the designated caregiver cannot be located to invite to participate, an invitation letter with opt-out postcard will be mailed to them.

Informed Consent

For Aim 1, there are special informed consent considerations in this pragmatic SW-CRT: the hospital clinical unit is the level of randomization, the intervention is of low risk and will be implemented as the standard of care for the whole clinical unit, and data for our primary outcome and related outcomes derived from the EHR are ascertained from existing sources. Thus for this aspect of our proposal, we will seek a waiver of individual informed consent and HIPAA authorization after careful review of the criteria to do so as we have previously done successfully in prior studies. The research involves no more than minimal risk to the subjects as described above. We do not believe the waiver will adversely affect the rights and welfare of the subjects. As a pragmatic trial of thousands of hospitalized patients and clinicians, this research could not practicably be carried out without the waiver nor without access to and use of PHI of patients.

For Aim 2a, we will seek a waiver of individual informed consent and HIPAA authorization due to the fact that this is a low risk activity (chart review), and the target population is incapable of consent due to a diagnosis of ADRD/Delirium.

For Aim 2b, verbal informed consent will be obtained for the phone survey. The caregiver survey should take less than fifteen minutes.

Natural Language Processing (NLP) Data Collection

Over the course of the study, we will review the charts for all enrolled participants. For Aim 1 and Aim 2a, the inpatient EHR records (including those with ADRD/Delirium) will be analyzed (approximately 15,000 patients across both sites).

Initial NLP analyses will be done locally at each data collection site (BMC and Northwell) using software that was developed at DFCI for this purpose. The results of that initial analysis will be coded and sent as a HIPAA LDS via HIPAA approved cloud folders such as Box.com to our NLP partners at DFCI. Each site will retain a local mastercode file that will not be shared with anyone outside the institution. Patients will be assigned a unique identifier that will be used on datasets shared with DFCI.

DFCI will have a reliance agreement in place with BUMC and Data Transfer Agreements in place with both BMC and Northwell.

Every 2 months (the size of each step; 1 baseline + 7 steps = 8 data transfers) the outcomes of interest using NLP will be transferred to our data collection site (DFCI). Data on the following outcomes will be collected until the end of the study period.

- ACP discussion (e.g., goals-of-care discussion, advance directive, MOLST/POLST, code status, etc.)
- Resuscitation preferences
- Palliative care consults
- Hospice Use
- Health care proxy discussion

As stated above, direct identifiers will be held at each respective site (BMC researchers can see BMC identifiers but not North Shore University Hospital's identifiers, and vice versa.) The risks will be minimal as the data will be stored and analyzed on a HIPAA secure cluster at each site. None of the data will be stored in paper form. The data and identifiers will be kept for seven years after the end of the study period on the HIPAA secure cluster computer at each site. After the seven years, all HIPAA identifiers and all linking codes will be permanently destroyed in accordance with regulation.

NLP Validation

Prior to the use of NLP for outcome assessment in this trial, we will entrain and validate the NLP process for each of our two study sites. Specifically, we will use historic note data from a sample of 20 patients from each site who meet enrollment criteria. We will then measure the validity of this process by comparing results from human assisted NLP to a human chart review. The goal of the keyword library validation process is to ensure that the keyword library and abstraction guidelines accurately represent the language used to communicate information associated study outcomes. The semi-automated note annotation process will be cross-validated across both sites. Clinical notes will be the substrate of this process and must be requested from each site's clinical data warehouse.

Each site will ensure that the appropriate IRB and Data Sharing protocols are in place before this activity begins.

Chart Review

EHR data will be extracted by manual chart review on all Aim 2a patients whose caregiver completes a survey (2b). This survey will be limited to the inpatient stay that generated the survey, and include the following elements for collection of secondary outcomes:

- DNR/DNI order
- MOLST/POLST filed
- Resuscitation/Intubation preferences
- Health Care Proxy specified
- Palliative Care Consult during hospitalization

- Discharge Disposition

A detailed chart review instrument is attached to the protocol.

Withdrawal

We do not anticipate any circumstances where the caregiver will withdraw from participation in the study. Study staff will make clear to the caregiver that participation is entirely voluntary and may be withdrawn at any time.

Masking

Due to the nature of the intervention, participants and staff will not be blinded to the intervention.

The NLP outcomes adjudication process is not fully automated in this study. We are doing a human-assisted NLP process in which a staff member validates the text presented in the software as a possible outcome. For NLP analysis, the following steps will be taken to ensure blinding to study step assignment by the staff member doing the NLP outcome attribution:

- Prior to adjudication activities, names will be coded
- Annotation will be performed in large batches with all patients enrolled who have clinical notes to that point.
- NLP notes for adjudication will not be grouped by Study ID when presented to annotators. Each note will be annotated individually, without reference to concepts contained in other notes annotated before or after.
- When possible, a staff member who did not enroll the participants will perform the annotation.

Caregiver Surveys

Caregivers will be surveyed using a REDcap survey. The REDCap project will be hosted by BUMC, both sites will enter data into the same project. All subjects will be assigned a unique identifier that will be entered into REDCap. All other PHI will be retained in a linking file that is not shared outside the institution.

Caregiver data will be linked with the associated patient EHR data, but this linking file will be kept locally, and only HIPAA LDS will be shared with other sites included on this protocol.

Costs/Payment

There are no costs to subjects for participating in this study.

Caregivers will be compensated \$50 for completing the survey.

10 Assessment of Safety and Data Safety Monitoring Plan (DSMP)

